CT of the chest / abdomen / pelvis 						
Hematology 	X	X	X	X	X	X
Serum chemistries 	X	X	X	X	X	X
Pregnancy testing 	X 				X 	
T-cell Repertoire Studies 	X 					
Comply with RevAssist® and S.T.E.P.S.® program	X					
Response assessment 	X					
Record adverse events 	X		X			X
Perform drug accountability	X					
Prescribe and dispense study drugs for next cycle 	X					

An unscheduled visit can occur at any time during the study. Source must be maintained for these unscheduled visits. The date for the visit and any data generated must be recorded on the appropriate CRF. Source documents for these unscheduled visits must also be maintained.

Procedure	Rituximab administration Cycles 7, 13, and 19				For all other cycles 8 and beyond 	Discontinuation From Protocol therapy
	Day 1	Day 8	Day 15	Day 22	Day 1	
Medical history assessment	X				X	
Interim history	X	X	X	X	X	
Physical examination, vital signs, weight	X	X	X	X	X	X
ECOG performance status	X	X	X	X	X	X
Lymph node, spleen and liver assessment by physical exam 	X	X	X	X	X	
Bone marrow assessment 						
BlyS/BAFF Analysis 	X				X 	
Peripheral Blood Cell Subset Analysis 					X 	
CD4/CD8/CD56 cell count						X
CT of the chest / abdomen / pelvis 	X				X 	X
Hematology 	X	X	X	X	X	X
Serum chemistries 	X	X	X	X	X	X
Pregnancy testing 	X 		X 		X 	X 
Comply with RevAssist® and S.T.E.P.S.® program	X				X	
T-cell Repertoire Studies 					X 	
IFE, beta-2-microglobulin, DAT	X				X 	
Response assessment 	X				X 	X
Record adverse events 	X	X	X	X	X	X 
Perform drug accountability	X				X	
Prescribe and dispense study drugs for next cycle 	X				X 	
Rituximab administration	X 	X 	X 	X 		
MRD status – peripheral blood assessment	X				X 	
Obtain Follow-Up anti-cancer treatments						F/u phase : Q 3 months
Obtain Follow-Up survival information						F/u phase : Q 3 months

 ≤ 28 days from baseline (First day study drug administration)

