-  After cycle 24, clinic visits (and the corresponding assessments) are only required every 3rd cycle (e.g. Cycle 24, 27, 30, etc.). For any non-clinic visit treatment cycles (e.g. Cycle 25, 26, 28, 29, etc.), subjects must still meet all requirements for the initiation of a new treatment cycle, including compliance with the RevAssist® and S.T.E.P.S.® programs, and all pregnancy testing and pregnancy risk counseling requirements. Hematology assessment (see number 7) will be done locally as required for the initiation of a new treatment cycle.
-  CT scans should be done every six months for three years, and every twelve months thereafter. Response assessment and MRD assessment should be performed every six months subsequent to Cycle 24. Patients whose blood counts meet criteria of a CR should undergo a CT scan within 4 weeks. If CT scan supports a response of CR, then bone marrow examination and peripheral blood MRD assessment should be performed within 4 weeks.
-  An additional safety assessment will be done 28 days (+/- 2 days) following the last dose of study drug.
-  Only enough thalidomide and lenalidomide for 1 cycle of therapy may be provided to the patient each cycle. For non-clinic visit treatment cycles subsequent to Cycle 24 (e.g. Cycle 25, 26, 28, 29, etc.), study drug will be shipped to the subject at the start of each cycle.
-  Physical examination of lymphadenopathy, spleen and liver will be performed on Days 1, 8, 15, and 22 of Cycles -1, 1, 2, 3,4 and 5 to assess for tumor flare reaction, and on Day 1 of subsequent cycles starting with cycle 5 to assess response.
-  CLL Flow Cytometry should include markers for diagnosis and prognosis: CD5, CD19/CD20, CD23, CD38, sIg, and zap-70, by immunohistochemistry. Also IgVH Mutation Analysis, Purified CLL cell interphase FISH, beta 2 microglobulin
-  Rituximab administration starting with Cycle 1 and then every 6th cycle through Cycle 19 (i.e. 7, 13, and 19) on Days 1, 8, 15 and 22.
-  Metabolimics on Days 1 and 15 prior to study drug administration for Cycles -1 and 1.
-  T-cell Repertoire Studies: samples will be collected prior to treatment on cycle -1 and prior to cycles 6, 12, and 24 and evaluated for T-cell Repertoire

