7. Patients who fulfill all of the criteria for CR, including marrow examination, but who have persistent anemia or thrombocytopenia, or neutropenia unrelated to CLL but related to drug toxicity will be characterized as CR with incomplete marrow recovery (CRi). These patients will be followed in order to determine whether their prognosis differs from

patients in CRs or PRs.

11.2 **Partial response:** any response less than a complete response but still meeting the following criteria:

1. 50% decrease in peripheral blood lymphocytes from the pre-treatment value.
2. 50% reduction in lymph node size by CT examination as measured by the sum of the products of up to 6 lymph nodes, or in one lymph node diameter if only a single lymph node is present.
3. No increase in the size of any lymph node, and no new enlarged lymph nodes, by CT examination.
4. 50% reduction in the size of the liver and / or spleen by CT examination
5. Blood counts must show one of the following:
  - a) neutrophil count  $\geq 1500/\text{mm}^3$  or 50% improvement over baseline without the use of growth factors.
  - b) hemoglobin  $> 11.0 \text{ gm/dL}$  or 50% improvement over baseline without transfusions or erythropoietin support.
  - c) platelet count  $> 100,000/\text{mm}^3$  or 50% improvement over baseline without transfusions.

11.3 **Progressive disease:** any of the following characteristics:

1. Progressive lymphadenopathy, as defined by:
  - a) Appearance of any newly enlarged lymph nodes to  $> 1.5 \text{ cm}$ .
  - b) An increase by 50% or more in greatest diameter of any previous site of disease. For a lymph node of 1 to 1.5 cm must increase by at least 50% to a size greater than 1.5 cm. A lymph node greater than 1.5 cm in diameter must increase to more than 2.0 cm in diameter.
  - c) An increase of 50% or more in the sum of the products of diameters of multiple lymph nodes.
2. An increase in liver or spleen size by 50% or more or the appearance of new hepatomegaly or splenomegaly.
3. An increase in the number of blood lymphocytes by 50% or more with at least 5000 B lymphocytes  $/\text{mm}^3$ .
4. Transformation to a more aggressive histology.
5. Occurrence of cytopenias attributable to CLL, excluding those related to therapy or autoimmune phenomenon. The progression of any cytopenia is defined by:

- a) decrease in Hb by more than 2 g/dL or to less than 10 g/dL.
- b) decrease in platelet counts by more than 50% or to less than 100,000/ mm^3.

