11.4 **Stable disease:** patients who have not achieved a CR or a PR, and who have not exhibited progressive disease, will be considered to have stable disease.

11.5 **Relapse:** patients who has previously achieved a CR or PR, but after a period of 6 or more months, demonstrate evidence of disease progression.

11.6 **Refractory disease:** disease progression within 6 months of the last treatment.

11.7 **Duration of response definitions:**

1. **Duration of response:** from the end of the last treatment until evidence of progressive disease.
2. **Time to response:** interval from the first treatment day to the date response first identified.
2. **Progression-free survival:** interval between the first treatment day and the first sign of disease progression.
3. **Event-free survival:** interval between the first treatment day to the first sign of disease progression, treatment for relapse, or death, whichever occurs first.
4. **Survival duration:** interval between the first day of treatment and death

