### 13.2 Datasets to be analyzed

Primary Endpoint:

- Overall response rate (CR + PR)

Secondary Clinical Endpoints:

- Progression Free Survival
- Duration of response
- Time to response
- Overall survival
- Toxicity profile

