### 13.3 Statistical Methodology

Primary Endpoint:

- The primary endpoint of response rate (overall, CR, PR) will be estimated and a 95% confidence interval will be estimated via binomial proportions

Secondary Endpoints:

- With adequate follow-up time, progression-free survival (PFS) will be assessed by Kaplan-Meier survival analysis and 95% confidence intervals will be calculated using Greenwood's formulae. PFS will be defined as the time from the first treatment day until objective or symptomatic progression (or until date of last follow-up if no progression).
- Duration of Response: from the end of the last treatment until evidence of progressive disease.
- Time to Response
- Overall Survival
- The frequency of subjects experiencing toxicities will be tabulated. Toxicities will be assessed and graded according to CTCAE v4.0 terminology. Exact 95% confidence intervals around the toxicity proportions will be calculated to assess the precision of the obtained estimates.

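### PFS is defined on progression alone, so read literally it censors deaths without progression and estimates time to progression

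*Combined protocol and SAP*

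**What the plan says.** PFS is defined twice. Section 11.7 gives it as the "interval between the first treatment day and the first sign of disease progression". Section 13.3 runs the time "until objective or symptomatic progression (or until date of last follow-up if no progression" and estimates it by Kaplan-Meier with Greenwood intervals. Neither definition mentions death.

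The same list in Section 11.7 defines event-free survival, which ends at "disease progression, treatment for relapse, or death, whichever occurs first". Event-free survival does not appear under "Secondary Clinical Endpoints" in Section 13.2, in the endpoint lists of the Schema and Section 1.4, or among the methods in Section 13.3.

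Section 13.3 counts symptomatic as well as objective progression. Section 11.3 defines progressive disease as "any of the following characteristics" and then lists lymph nodes, liver or spleen, blood lymphocytes, transformation and cytopenias. It has no symptom criterion.

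For the period after treatment ends, the Section 10 calendar has rows headed "Obtain Follow-Up anti-cancer treatments" and "Obtain Follow-Up survival information", each every three months. Section 5.7 says that patients who stop treatment are followed for 30 days.

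**The concern.** PFS is ordinarily understood to end at progression or death, whichever comes first. Under the rule in Section 13.3, a patient who dies without progressing falls under the no-progression clause and leaves the analysis without an event. The estimate is then time to progression with deaths censored, and the name PFS does not tell the reader so. No listed endpoint combines progression and death.

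The effect runs one way: it makes the result look the same or better, never worse, when date of death is used as last follow-up. Symptomatic progression adds a second uncertainty, because an event could be called under Section 13.3 that Section 11.3 does not recognise.

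**Working it through.** The plan states no PFS estimate, event count or power, so there is no PFS figure to reproduce. The check has three parts: the wording, the direction of the effect, and its size in an example.

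**1. Wording**
- PFS, Section 11.7: the event is progression; death is not named.
- PFS, Section 13.3: the event is objective or symptomatic progression; otherwise the time ends at last follow-up; death is not named.
- Event-free survival, Section 11.7: progression, treatment for relapse, or death.
- Section 5.6: death and disease progression are separate reasons for ending treatment.

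The plan names death where it means to count it. Nothing makes death a PFS event.

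**2. Direction**

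Take the date of death as last follow-up. A patient who dies leaves the risk set on the same day whether the death is censored or counted, so the risk sets are identical in the two analyses. Counting a death only adds a factor (1 − 1/n), where n is the number at risk on that day:

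PFS counting death = (curve with deaths censored) × product of (1 − 1/n) over deaths without progression.

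Every added factor is below 1. The curve as defined is therefore never below PFS that counts death, and the two are equal if there are no such deaths.

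**3. Size**

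Inputs: N = 24 (Schema and Section 13.1). Assumed: complete follow-up to month 24, 9 progressions, and k deaths without progression.

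- Deaths counted: (24 − 9 − k)/24 = (15 − k)/24.
- Deaths censored, all before the first progression: (15 − k)/(24 − k).
- Deaths censored, all after the last progression: 15/24.

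| k | Deaths counted | Censored, deaths first | Censored, deaths last | Gap |
|---|---|---|---|---|
| 0 | 15/24 = 0.625 | 0.625 | 0.625 | 0 |
| 1 | 14/24 = 0.583 | 14/23 = 0.609 | 0.625 | 0.025 to 0.042 |
| 2 | 13/24 = 0.542 | 13/22 = 0.591 | 0.625 | 0.049 to 0.083 |

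Check against step 2 for k = 1: 14/23 × 23/24 = 14/24, and 15/24 × 14/15 = 14/24.

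The upper end of the gap is k/24 whatever the number of progressions m, because (24 − m)/24 − (24 − m − k)/24 = k/24. The lower end depends on m only moderately. With 8 progressions and one death it is 15/23 − 15/24 = 0.652 − 0.625 = 0.027, against 0.025 with 9.

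For scale, with complete follow-up the Greenwood standard error is √[S(1 − S)/24]. At S = 0.583 this is √(0.583 × 0.417/24) = 0.101, so one death moves the estimate by about a quarter to two fifths of a standard error (0.025/0.101 and 0.042/0.101).

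**4. Primary endpoint**

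The two-stage rule in Section 13.1 (11 patients, then 24; success at 18 or more responders) has an exact type I error of 0.093 at a 60% response rate and power of 0.801 at 80%, as the plan intends. It does not use PFS.

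**The case against.** The plan never says that deaths are censored. The defect could be called a missing rule, which an analyst would fill by convention. It is true that censoring is an inference. But the clause in Section 13.3 covers every patient without progression, and the neighbouring event-free survival definition shows that death was named where it was meant to count. Convention does not settle what this text instructs.

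PFS here is secondary, carries no hypothesis test, and is to be analysed only once follow-up is adequate. Deaths still appear in overall survival. The shift from one death is well inside the sampling error. All of this stands, and it limits the importance of the point. It does not remove an error of known direction that a few words would correct.

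A reader might go further in three ways that the documents do not support.

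- **A likely size from the background section.** Section 2.4 gives a median life expectancy of almost nine years and says that 70% of patients die of disease-related causes. Cause of death is not the same as death without Section 11.3 progression: a disease-related death can come without recorded progression, and an unrelated death can come after it. No document gives the progression rate or the rate of deaths without progression. Only the conditional count arithmetic is sound.
- **No disease assessment off treatment.** Footnote 12 of the calendar says "CT scans should be done every six months for three years, and every twelve months thereafter" and is silent on whether this continues after discontinuation. The calendar does mark CT, haematology, physical examination and response assessment at discontinuation, and treatment otherwise continues to progression. The open question concerns only patients who stop for another reason, and its effect cannot be computed.
- **Misleading comparison with outside PFS figures.** The documents cite no PFS benchmark, so this cannot be shown from them.

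**Conclusion.** The point holds. As written, the endpoint called PFS is time to progression, with deaths before progression censored under a literal reading of Section 13.3. Event-free survival does not fill the gap: it is neither listed nor analysed, and it also counts treatment for relapse.

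With the assumed 9 progressions among 24 fully followed patients, the 24-month estimate is too high as PFS by 2.5 to 4.2 points for one death without progression and by 4.9 to 8.3 points for two. With no such deaths the gap is zero. The direction rests on one condition, that last follow-up for a patient who dies is the date of death. If an earlier contact were used, that patient would leave the risk set sooner and the ordering need not hold at every time point.

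It would be wrong to infer that the trial's main conclusion is at risk. The response-rate decision and the sample size do not depend on PFS. This should be corrected because it is a labelling error of known direction in a reported endpoint and is cheap to put right.

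**What to change.** - In Sections 11.7 and 13.3, define PFS as the time from first treatment to progression or death from any cause, whichever comes first. Censor patients with neither at their last disease assessment. If the sponsor wants progression only, rename the endpoint time to progression in every list.
- Use the Section 11.3 criteria for progression in both sections. Either align symptomatic progression with them or remove it.
- Reconcile the 30-day follow-up in Section 5.7 with the three-monthly follow-up in Section 10. Counting death needs no new data only if the three-monthly contact applies, because under Section 5.7 alone later deaths would not be collected.

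Listing event-free survival as well is possible but does not replace the correction, since it is a different endpoint.

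The cost is wording. Reported PFS may be slightly less favourable. The sample size of 24 and the 18-of-24 rule do not change.

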### **5.6 Duration of Therapy and Criteria for Removal From Study**

- Treatment will continue until the occurrence of any of the following events.
- Disease progression (excluding tumor flare)
- Adverse event(s) that, in the judgment of the Investigator, may cause severe or permanent harm or which rule out continuation of the treatment regimen.
- Discontinuation of thalidomide or lenalidomide for any reason. (Note, patients who are unable to tolerate rituximab infusions may still continue on the protocol.)
- Major violation of the study protocol.
- Withdrawal of consent
- Lost to follow up
- Death
- Suspected pregnancy or positive pregnancy

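### PFS is censored at an undefined last follow-up date, although no disease assessment is scheduled after the discontinuation visit

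*Combined protocol and SAP*

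**What the plan says.** **The rule.** Section 13.3 states that "progression-free survival (PFS) will be assessed by Kaplan-Meier survival analysis", with Greenwood confidence intervals. The clock runs from the first treatment day "until objective or symptomatic progression (or until date of last follow-up if no progression". Section 11.7 defines PFS as the "interval between the first treatment day and the first sign of disease progression" and gives no censoring rule. Neither section mentions the last disease assessment or the start of another therapy.

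**Stopping without progression.** Section 5.6 ends treatment for several reasons other than progression, among them "Discontinuation of thalidomide or lenalidomide for any reason". Progression is therefore not the only common way off treatment.

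**What is collected afterwards.** The discontinuation column in Section 10 has a physical examination, blood tests, CT and a response assessment. Its follow-up-phase entries are "Obtain Follow-Up anti-cancer treatments" and "Obtain Follow-Up survival information", each every three months with no end date. Footnotes add a safety assessment at 28 days and post-dose pregnancy tests. No CT, node examination, blood count or response assessment is entered for the follow-up phase.

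**How long follow-up lasts.** Section 5.7 says 30 days. Section 5.3 sets a six-month minimum for contact without giving its content. Section 10 says every three months.

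**The related endpoint.** Section 11.7 also defines event-free survival, ending at the "first sign of disease progression, treatment for relapse, or death, whichever occurs first". It is not among the secondary endpoints in Sections 1.4 or 13.2.

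**The concern.** A Kaplan-Meier estimate is sound only if patients counted as at risk are also observed for the event. Suppose a patient stops for toxicity at month 6, starts another CLL regimen at month 9 and is known to be alive at a month-36 contact. With no progression recorded and the calendar followed, that patient is carried as progression-free to month 36. The last scheduled disease assessment was at month 6, and any control of disease after month 9 may be due to the second regimen.

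Such patients enlarge the denominator but contribute no scheduled events, so the curve sits too high. The excess grows with the rate of stopping for toxicity. The trial's hypothesis is that alternating dosing is better tolerated and allows longer therapy, so this error would make a poorly tolerated regimen look better on PFS. The issue here is the censoring date of living patients; how deaths enter PFS is a separate matter.

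**Working it through.** **The plan's own figures.** The only design calculation is for response. The two-stage rule (stop at 6 or fewer of 11; success at 18 or more of 24) reproduces by exact binomial: type I error 0.0930 at 60% and power 0.8015 at 80%. An exhaustive search returns the same design as minimax, so N = 24 stands. No sample size, event count or rate is stated for PFS, so what follows is illustrative.

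**Assumptions (not in the documents).** Exponential progression with median 24 months, so λ = ln 2 / 24 = 0.02888 per month. Stopping without progression occurs at a constant rate μ = 0.01, 0.02 or 0.03 per month, independent of progression.

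**Reading A: calendar follow-up, no progression captured after stopping.** Stopped patients stay at risk with no events, so the estimate tends to

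KM(t) = 1 − [λ/(λ+μ)] × [1 − exp(−(λ+μ)t)].

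For μ = 0.02 and t = 24:
- λ/(λ+μ) = 0.02888/0.04888 = 0.5908
- exp(−0.04888 × 24) = 0.3094
- KM(24) = 1 − 0.5908 × 0.6906 = 0.592

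The true value is exp(−λ × 24) = 0.500. At 36 months the same formula gives 51.1%, against a true 35.4%.

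**Reading B: half of the later progressions captured, with correct dates.** If a fraction q is captured, the excess is multiplied by (1 − q). For μ = 0.02 and q = 0.5, 9.2 × 0.5 = 4.6 points.

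**Reading C: follow-up ends at 30 days (Section 5.7).** The risk set at t holds those on treatment, a(t) = exp(−(λ+μ)t), plus those who stopped within the past month, b(t) = [μ/(λ+μ)] × [exp(−(λ+μ)(t−1)) − a(t)], with t−1 replaced by 0 in the first month. The apparent hazard is λ·a/(a+b), integrated numerically to 24 months.

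**Censoring at the last disease assessment.** Only patients still being assessed are at risk, so the estimate tends to exp(−λt), the true curve. This follows from the assumed independence of stopping and progression.

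| Stopping per month | Stopped without progression by month 24, of 24 patients | True 24-month PFS | A: none captured | B: half captured | C: 30 days |
|---|---|---|---|---|---|
| 1% | 3.7 | 50.0% | 54.9% | 52.5% | 50.3% |
| 2% | 6.8 | 50.0% | 59.2% | 54.6% | 50.7% |
| 3% | 9.3 | 50.0% | 62.9% | 56.4% | 51.0% |

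The second column is 24 × [μ/(λ+μ)] × [1 − exp(−(λ+μ) × 24)].

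**Sensitivity to the median.** With a true median of 36 months and 2% per month stopping, Reading A gives 70% against 63% at 24 months, and 63% against 50% at 36 months.

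**The case against.** The strongest reply has four parts.

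1. **Follow-up may be short.** Section 5.7 says 30 days, and then the bias is about 1 point. This stands as a limit on size, but Sections 5.3 and 10 say otherwise and nothing ranks the three. An estimate that depends on which section the analyst follows is itself a defect.

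2. **Progression can still come to light.** A reader might infer that progression cannot be recorded once treatment stops. The documents do not support that. The Section 13.3 event includes symptomatic progression, which needs no scheduled CT. Duration of response and refractory disease in Section 11 both presuppose that progression is known after the last treatment. The CT interval in calendar footnote 12 is not expressly limited to treated patients, although no follow-up-phase entry carries it. A new regimen reported at a three-monthly contact also invites the question. What can fairly be said is that ascertainment after stopping is unscheduled, so Reading A is an upper bound under the stated rates.

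3. **PFS carries no decision.** It is secondary, with no threshold or comparator. With 24 patients and no censoring, the standard error near 50% is √(0.5 × 0.5/24) = 10.2 points, giving a 95% interval of about ±20. Toxicity is reported directly with exact intervals, so poor tolerability would not be hidden. This stands and lowers the priority. It does not excuse a bias of known direction, because the confidence interval reflects sampling error only.

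4. **The alternative has its own assumption.** Censoring at the last assessment is unbiased only if stopping is unrelated to prognosis. This also stands, and is why a sensitivity analysis is needed.

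**Conclusion.** The concern holds. Section 13.3 names a censoring date that the rest of the document does not define. Under the calendar's follow-up, it credits unassessed time, including time on later therapy, as progression-free, and the bias is upward.

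Its size cannot be fixed from the documents. On the assumed 24-month median and 1–3% per month stopping, 24-month PFS would be up to 55–63% instead of 50%. The excess is about half that if half of later progressions are captured, and about 1 point if follow-up ends at 30 days.

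A reader might take the upper figures as the expected error, or infer that the trial's conclusion is at risk. Neither follows. The figures require calendar follow-up with no capture after stopping, and the decision on response (18 or more of 24) does not use PFS. The point should be fixed before PFS is analysed, since choosing the rule after seeing the data would be data-dependent.

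**What to change.** 1. In Sections 13.3 and 11.7, censor living patients without progression at their last disease assessment on or before the start of any new anti-cancer treatment.
2. Reconcile Sections 5.3, 5.7 and 10 on the length, frequency and content of follow-up.
3. At the existing three-monthly contact, also record whether progression has been diagnosed, and when.
4. As a sensitivity analysis, report an event-free survival in which any new CLL treatment counts as an event. State that this modifies the Section 11.7 definition, which counts only treatment for relapse. The treatment dates can come from the contacts already scheduled.

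**Cost.** A few sentences of text and one added item (status and date) at a contact already planned, with no new visits and no change to sample size. The statistical price is more censoring, a probably less favourable curve, and reliance on stopping being non-informative. The sensitivity analysis probes that reliance but does not remove it.

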## 5.2 Investigational Study Drug Combination (THRIL)

### **Starting with Cycle 1:**

#### **A cycle is 28 days:**

Thalidomide 50 mg every ODD day, days 1-28 every 28 days

Lenalidomide every EVEN day, days 1-28 every 28 days at the dose indicated above and with possible dose escalation as described in 5.1.

Rituximab 375 mg/m^2 IV on days 1, 8, 15 and 22 (+/- 2 days) starting with Cycle 1 and then again on the same weekly x 4 schedule every 6th cycle through Cycle 19 (Cycles 7, 13, and 19).

Responses will be assessed at monthly intervals using the response criteria outlined by the IWCLL update of the 1996 NCI-Working Group criteria. Patients will remain on treatment until they demonstrate disease progression or unacceptable toxicity. It will be important for the investigator to differentiate disease progression from tumor flare. While no strict criteria can be established for this distinction, rapid changes in clinical status that occur within four weeks of a dose escalation are likely to be tumor flares and should be treated as such.

Tumor flare has been described with both thalidomide and lenalidomide treatment. Therefore, patients should be monitor closely for signs and symptoms of tumor flare for four weeks after each increase in dose. Prophylaxis for (TFR) is not recommended. Grade 1 TFR may be treated with NSAIDs (i.e. ibuprofen 400-600 mg orally every 4-6 hours as needed). TFR  $\geq$  Grade 2 may be treated with corticosteroids. Narcotic analgesics may be added as needed for pain control in subjects experiencing  $\geq$  Grade 2 tumor flare. If corticosteroids are used, the following dosage schedule is

recommended: prednisone 20 mg PO QD x 7 days followed by 10 mg PO QD x 7 days. (See Appendix D: Cairo Bishop Tumor Lysis Definition and Grading Criteria.)

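### Duration of response is counted from the end of treatment, but the oral drugs have no planned end, so the variable does not measure how long responses last

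*Combined protocol and SAP*

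**What the plan says.** Duration of response is a secondary endpoint in 1.4 and 13.2. Section 13.3 defines it: "Duration of Response: from the end of the last treatment until evidence of progressive disease". Section 11.7 has the same start and end: "from the end of the last treatment until evidence of progressive disease". No section gives another start date, a censoring rule or an estimation method for it. For PFS, by contrast, 13.3 names Kaplan-Meier and says what to do with patients who have not progressed.

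Section 11.7 defines time to response as "interval from the first treatment day to the date response first identified", so the plan already needs a date of first response for every responder.

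On treatment length, section 5.2 says: "Patients will remain on treatment until they demonstrate disease progression or unacceptable toxicity". Section 5.6 lists the stopping events. They include progression and "Discontinuation of thalidomide or lenalidomide for any reason", and no cycle limit appears among them. The study calendar in section 10 provides for long treatment. Footnote 14 says: "For non-clinic visit treatment cycles subsequent to Cycle 24 (e.g. Cycle 25, 26, 28, 29, etc.), study drug will be shipped to the subject". Footnote 12 says: "CT scans should be done every six months for three years, and every twelve months thereafter". Only rituximab has a planned last course, in Cycle 19.

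**The concern.** Counting from the end of treatment can work for a fixed course, where treatment ends on a planned date that does not depend on progression. Here progression is itself a reason to stop, so for many responders the start and end of the interval could be nearly the same day. The variable then records when drug was stopped, not how long the response held.

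It also orders patients the wrong way. The Schema and section 2.5 hope that better tolerability will allow longer therapy and better responses. Under the written definition, for a response of given length, the longer the patient stays on drug the shorter the recorded duration.

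Finally, it does not fit the other endpoints. For a responder with observed progression, PFS minus time to response is the time spent in response. The written duration is a different quantity. A published figure under this label would be read as the usual one.

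**Working it through.** The plan states no figure for duration of response (no median, event count or precision), so there is nothing to reproduce. The check applies the written rule and a response-based rule to the same example patients.

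**Inputs from the documents**
- Cycles last 28 days, and Cycle -1 precedes Cycle 1 (5.1).
- Partial response needs CT: "50% reduction in lymph node size by CT examination" (11.2). The first on-treatment CT mark in the calendar is Cycle 7 Day 1.
- The last calendar column with CT and response assessment is discontinuation. After that the calendar lists only anti-cancer treatment and survival, every 3 months.

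**Assumed:** all patient dates below, and no cycle delays.

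**Day count.** With Cycle -1 Day 1 as day 1, CnDk = 29 + 28(n - 1) + (k - 1).
- C7D1 = 29 + 168 = 197
- C12D28 = 29 + 308 + 27 = 364
- C23D28 = 29 + 616 + 27 = 672
- C24D1 = 29 + 644 = 673
- C36D1 = 29 + 980 = 1009

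**Responder who progresses on drug.** Response on day 197, last dose on day 672, progression on day 673.
- Time in response: 673 - 197 = 476 days (15.6 months).
- As written: 673 - 672 = 1 day.
- Cross-check: PFS (673 - 1 = 672) minus time to response (197 - 1 = 196) = 476 days.
- The written value depends on the gap between last dose and recorded progression. A 28-day gap either way moves it to about +0.9 or -0.9 months, so it can even be negative.

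**Responder still on drug.** Response on day 197, still in response on day 1009.
- Time in response so far: 1009 - 197 = 812 days (26.7 months), a censored observation.
- As written: no start date, so no value and no censored time.

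**Responder who stops before progression.** Response on day 197, drug stopped on day 364, disease assessed at discontinuation.
- Response-based: 364 - 197 = 167 days, censored at that assessment.
- As written: all 167 days on drug are discarded and the clock starts at day 364.

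**Ordering.** Take one response from month 6 to month 30, with the progression date known. Its length is 24 months. As written it is 30 - 12 = 18 months if drug stopped at month 12, 30 - 24 = 6 months if stopped at month 24, and 0 if drug continued to progression.

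**Could last treatment mean rituximab?** No section says so. If it did, the last planned infusion is C19D22 = 29 + 504 + 21 = 554, and the first patient would score 673 - 554 = 119 days, still not 476.

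**The case against.** The strongest reply is that little is lost. The endpoint is descriptive, with no hypothesis, power or decision rule attached. For responders who progress on drug, the dates of first response and progression are already needed for time to response and PFS, so the usual duration can be derived without new data. That stands, and it limits the seriousness of the point. It does not rescue the stated rule, which an analyst following the plan would have to apply.

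Two stronger conclusions are tempting, and the documents do not support them.

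- A reader might infer that the reported median must come out near zero or not be reached. That depends on how many responders progress on drug, remain on drug, or stop early and progress later. The documents do not allow these shares to be derived, and the last group gets clearly positive values. The plan also names no Kaplan-Meier analysis for this endpoint.
- A reader might infer from the 30 days in 5.7 that everyone who stops early is censored within a month. Section 5.3 mentions follow-up contact at a minimum of six months. Sections 11.5 and 11.6 use a six-month boundary that presupposes knowledge of later progression. The CT schedule in footnote 12 is not expressly limited to time on treatment. Capture of progression after discontinuation is therefore unclear; it is not shown to stop at 30 days.

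**Conclusion.** The definition is wrong as written and should be changed. The defect follows from the text of 11.7 and 13.3 set against 5.2, 5.6 and calendar footnotes 11, 12 and 14, and needs no assumption about the data. The sizes (476 days against 1 day, and 812 days against no value) are illustrations that rest on assumed dates and undelayed cycles. How far a summary across responders would be distorted cannot be derived from the documents.

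The effect is confined to this secondary endpoint. The sample size of 24, the rule to continue with 7 or more responders among 11, and the cut-off of 18 among 24 depend only on the number of responders and do not change.

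**What to change.** In both 11.7 and 13.3:

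1. Define duration of response, among responders, from the date CR or PR is first identified (the date that ends time to response) to progression.
2. Use the same progression event as PFS in 13.3. That event includes symptomatic progression, whereas the list in 11.3 has no symptom criterion. Ending duration at 11.3 alone would create a new mismatch.
3. State whether death without progression counts as an event or is censored.
4. Estimate by Kaplan-Meier, and censor responders without an event at their last disease assessment.
5. Report how many responders were censored after stopping treatment before progression.

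**Cost.** This is a rewording in two places, with no new visits and no change to the primary analysis. The start date does inherit the plan's differing statements on response timing: monthly in 5.2, every four weeks in 11, after Cycle 6 in 13.1, with CT every six months. One rule for dating first response should be stated.

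**Downside.** Censoring at discontinuation may be informative, because the calendar lists no disease assessment after that visit and 5.3 and 5.7 leave capture of later progression unclear. The count in item 5 lets a reader judge how much this matters.
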